3. METHODS

Semi-structured interviews

Semi-structured interviews will be used within this study to explore the views and experiences of parents and children who have had bone and joint infections. Parents and children will be interviewed together. Semi-structured interviews are characterised by:

- an interactional exchange
- a topic centred dialogue, but with a flexible structure
- an acknowledgement that within an interview context, meaning and knowledge is co-produced [1]

The interview guides for parents and children will be developed with reference to existing literature (e.g. qualitative work in this field, factors impacting on participation in RCTs, qualitative research interviews with children); by experts in the field including our Research Fellow, [name], and in consultation with our patient and public involvement contributors. The interview guide will be piloted with between three and five children and their parents, (although as is usual practice in qualitative research, these data will be included in the final analysis).

The interviews will be digitally recorded, with permission from the families and children, all identifying features will be omitted, and the recordings will then be transcribed by a professional transcribing agency. The transcriptions will then be returned to the qualitative researcher for analysis.

Sample and Consent

A purposive sample of children aged 0 to 16 years who have had bone and joint infection within the previous year will be identified from seven centres who have participated in the main Dinosaur service evaluation. The purposive sample strategy will be developed to address variation with regard to age, gender, and ethnicity. Parents/carers, and, where appropriate and consent has been obtained, young people, will be interviewed together with their parents. We anticipate that a sample size of thirty families should be sufficient, but will

continue sampling until data saturation is reached. [3] All families approached who agree to participate will be interviewed.

Inclusion criteria

- Parents and children from 3months to sixteen-years-old with osteomyelitis and septic arthritis
- who have been treated for bone and joint infections at seven sites identified below
- who have consented to take part in this qualitative study

Children and their parents at the following seven sites have participated in the main DINOSAUR study: Bristol Children's Hospital, Oxford Children's Hospital (University Hospitals Oxford NHS Trust), University Hospital Southampton NHS Foundation Trust, Imperial College Healthcare (St Mary's Hospital London), St George's Hospital London, Birmingham Children's Hospital and Liverpool Alder Hey Hospital. At the point of initial consent for participation in the larger study, participants (i.e. children and their families) were also asked if they would be willing to be contacted about possible participation in a smaller qualitative study. Once ethics and site specific approvals have been received, letters will be sent to those parents and children consenting to be contacted about the qualitative study, to include Participant Information Sheets. Potential participants will be invited to make contact with the research team if they are interested in hearing more. The qualitative researcher will make contact with interested parents and children to explain further about the study, answer any queries, and arrange to meet.

On meeting, any additional concerns/queries will be addressed, and if happy to continue, written consent will be received immediately prior to conduct of the interview.

4. TIME LINE

We anticipate contacting families early October 2014, with a view to organising interviews between October 2014 and January 2015.

5. DATA ANALYSES

As is usual in qualitative analysis, data collection and analysis will occur concurrently, in this instance using the constant comparative method. Analysis will move from the generation of initial 'in vivo' codes to more abstract, theoretical frameworks, which explain the vast majority of the data generated [2]. The qualitative research will also use memos to capture

analytic thoughts and ideas which will inform the analysis, and will also provide evidence of an audit trail, one of the strategies which can demonstrate the credibility of the analysis [4]

6. RESEARCH GOVERNANCE, MONITORING, ETHICS AND R&D APPROVAL

The research will comply with the Research Governance Framework and International Conference on Harmonisation Good Clinical Practice (ICH GCP).

The study will be sponsored by University Hospital Southampton NHS Foundation Trust, subject to the relevant governance approvals. The Sponsor will delegate appropriate responsibilities to the Chief Investigator, and to [name] (lead qualitative researcher) who will co-ordinate the study and will during pilot phase provide at least weekly supervision, and thereafter a minimum of two weekly supervision to [name].

There are some ethical considerations with this study that requires trained researchers not directly involved with the patients' medical care to have access to limited confidential information.

7. FINANCE

This study is supported by the NIHR HTA project 10/146/01 - Duration of intravenous antibiotic therapy for children with acute osteomyelitis or septic arthritis: a feasibility study

8. REPORTING AND DISSEMINATION

We will use the normal channels of journal publication and conference presentations. In addition, we are committed to ensuring that our research is available via open access and we will have a dissemination strategy that includes rapid web-based publishing of lay summaries once research articles have undergone peer-review and links to University and Trust press offices.

1.2 RCT process diagram and information

Possible trial design

In the past, patients with bone and joint infections stayed in hospital for up to 6 weeks, and were treated with intravenous antibiotics. This is what we could call the ‘text book’ treatment.

Nowadays, it is more common for patients to be given intravenous antibiotics at first, with a switch being made to oral antibiotics (tablets or medicine), when they start to get better. There has also been a move towards using less total antibiotic treatment, but the exact length of treatment varies within the UK and similar countries abroad.

[figure not shown]
At the moment, doctors do not have clear evidence about the best length of time for patients to stay on intravenous antibiotics, or on the signs of improvement that show a switch to oral antibiotics can be made.

Conducting a clinical trial would determine:

- The best length of the total antibiotic treatment and whether this could be shortened
- The best length of intravenous antibiotic treatment, and the signs of recovery needed before a switch to oral antibiotics can be made
- The best length of oral antibiotic treatment

The process for the trial is shown on the next page. This type of trial is called a randomised controlled trial. It compares two groups of people: one group who receive the new treatment and another group, who receive the standard treatment (this group is called the ‘control group’). The control group allows the researchers to see whether the treatment they are testing is any more or less effective than the usual or standard treatment. In a randomized controlled trial, the decision about which group a person joins is random (i.e. based on chance). A computer will decide rather than the researcher or the participant. Randomization ensures that the two groups are as similar as possible, except for the treatment they receive. This is important because it means that the researcher can be sure that any differences between the groups are only due to the treatment.

FIGURE 1: PROCESS FOR PROPOSED TRIAL

Some questions

- Who/where should study information come from?
- What information would you like?
- How long would you need to think/decide?
- Who would you talk to?
- How would you feel about being randomly allocated to a treatment arm?
- Thoughts about either treatment option?

Would you be willing for your child to take part in this trial?
Why?

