1. INTRODUCTION AND BACKGROUND

Osteomyelitis (OM) and septic arthritis (SA) are relatively unusual infections in children, however, they confer considerable morbidity. At present there is limited evidence and no UK or global consensus on how to optimally treat these infections with antibiotics. The DINOSAUR study (Duration of Intravenous Antibiotic Therapy for Acute Osteomyelitis and Septic Arthritis in a Paediatric Population) has 3 components to determine the feasibility of whether a trial of shortened courses of intravenous and oral antibiotics for the treatment of bone and joint infections in children will be feasible in the UK. (www.dinosaur-study.org.uk). The feasibility study comprises a service evaluation, Delphi survey and stakeholder meeting to establish consensus from the different clinical stakeholder groups, and a qualitative study to input young people and parent's views into the Delphi and stakeholder process.

Parents were consulted during the proposal application for the DINOSAUR study and agreed that a qualitative component engaging parents of children who had had bone and joint infections would be beneficial. This qualitative study incorporates parents' views and experiences into the question of whether a formal clinical trial will be feasible.

Historically patients with OM/SA have been treated with up to six weeks intravenous antibiotics as inpatients in hospital. It is now more common practice to treat paediatric OM/SA with intravenous antibiotics initially, and then switch to oral antibiotics once clinical improvement is seen, and the child is able to take and absorb oral antibiotics. An alternative has been the use of outpatient intravenous antibiotic therapy (OPAT) before the switch to oral medicines. The criteria for switching from intravenous to oral antibiotics, and the total duration of antibiotics varies between centres within the UK and internationally.

Diagnosis of OM/SA combines haematological and biochemical blood results, microbiological analysis of blood and tissue samples and imaging using plain x-rays, ultrasound and MRI scan. Treatment may include surgery, such as drainage of a joint, and drilling and decompression, although the mainstay of treatment is immediate, intravenous antibiotic therapy.

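### The adult and 13+ trial sheet uses a loaded label ('text book') and leaves 'standard' undefined just before asking about willingness to take part

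*Protocol*

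**What the plan says.** Protocol section 1.2 (RCT process diagram and information) opens with history: "In the past, patients with bone and joint infections stayed in hospital for up to 6 weeks", treated with IV antibiotics. The next sentence adds "This is what we could call the ‘text book’ treatment". The sheet then turns to the present: "Nowadays, it is more common for patients to be given intravenous antibiotics at first, with a switch being made to oral antibiotics". It adds that the length of treatment differs within the UK and abroad, and that "doctors do not have clear evidence about the best length of time for patients to stay on intravenous antibiotics".

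Further down, a randomised controlled trial is explained as a comparison of "one group who receive the new treatment and another group, who receive the standard treatment". The control group is there to show whether the tested treatment is "any more or less effective than the usual or standard treatment". The sheet closes with a list of questions, the last of which asks whether the parent would be willing for the child to take part, and why.

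Protocol section 1 gives the background position: "At present there is limited evidence and no UK or global consensus on how to optimally treat these infections with antibiotics". It tells the same history of up to six weeks of IV treatment without the 'text book' label.

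Protocol section 2, aim 3, makes willingness to be randomised to either arm one of the topics to be explored. In the adult and 13+ topic guide (section 1.3.5), the background sheet and process diagram are shown before question 13, and the interviewer works through the questions on the sheet with the family. Question 15b asks about willingness again after a risk and benefit card, and probes the reasons for any change from the first decision.

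**The concern.** A question about willingness to be randomised is informative when the respondent understands the two options and does not take the wording as a signal about which one is accepted. Two features of this sheet work against that.

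- **An authority label.** 'Text book' carries approval. It adds nothing to the description of past practice and is attached to one of the two kinds of treatment under discussion.
- **An undefined reference.** 'Standard', and later 'usual or standard', presupposes one accepted treatment. The sheet does not say what it is, and its own account of practice leaves more than one candidate.

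What is at stake is the interpretation of aim 3. If some families take 'standard' to mean prolonged IV treatment and others take it to mean the present IV-to-oral switch, their views on allocation refer to different trials. A reluctant or enthusiastic answer may then partly be a response to the labels. The first answer matters most, because question 15b treats it as the starting point from which change is probed.

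**Working it through.** No arithmetic applies. The expected thirty families are a saturation-based figure, and nothing in the point depends on it. The check is a comparison of the places that bear on the wording.

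**1. What 'text book' is attached to.** It follows directly on the sentence about stays of up to 6 weeks and is introduced by the words for past practice. It therefore describes long IV treatment as a historical regimen, not as a trial arm.

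**2. What 'standard' is attached to.** In the visible text, nothing. 'New' and 'standard' occur in the explanation of what a randomised trial is, and neither word is tied to longer or shorter IV treatment. Figure 1 is not available, so it cannot settle the matter either way.

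**3. Which treatment a reader could take as standard.** The sheet offers three statements:

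| Statement on the sheet | What it suggests is standard |
|---|---|
| Long IV treatment is 'text book' | Prolonged IV treatment |
| "Nowadays, it is more common for patients to be given intravenous antibiotics at first", then a switch to oral | The IV-to-oral switch |
| Length varies within the UK and abroad | No single standard |

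The three do not lead to one answer, so 'usual or standard' has no definite meaning for the reader.

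**4. Set against the protocol's position.** Section 1 says "At present there is limited evidence and no UK or global consensus on how to optimally treat these infections with antibiotics". A label implying an accepted reference treatment sits poorly with that. Section 1 conveys the same history without the label, so the label is not needed to tell it.

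**5. Position in the interview.** The willingness question is printed on the sheet itself. The guide has the sheet shown before question 13 and its questions worked through at that point. The first willingness answer therefore comes straight after the labels, and the second (15b) is compared with it.

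**6. Wording of the other tools.** The card in section 1.3.1 uses later and early switch, with longer and shorter IV as descriptions. The 8-12 years card in section 1.3.2 uses longer and shorter IV, with treatments A and B. The 8-12 topic guide (section 1.3.4) speaks of two different types of treatment. Of the materials that can be seen, only the section 1.2 sheet uses 'new' and 'standard'. The 8-12 process sheet is not shown, so nothing is claimed about it. Section 3 has parents and children interviewed together, so one family may meet both styles of wording.

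**7. Size.** The document gives no figure from which an effect of wording on willingness could be calculated.

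**The case against.** The case for leaving the sheet alone has several sound parts.

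- **The label is historical and hedged.** 'In the past' followed by 'nowadays' is a chronological account, and a past textbook regimen is compatible with a present lack of consensus. This stands. A reader might infer that the sheet contradicts section 1, but the text does not support that.
- **The arms are not labelled.** A reader might infer that the longer-IV arm is called standard and the shorter-IV arm new. The reading is natural, since section 1 describes a trial of shortened courses, but it joins two separate paragraphs. The visible text never makes the link.
- **Uncertainty is already disclosed.** The sheet says that "doctors do not have clear evidence about the best length of time for patients to stay on intravenous antibiotics" and that practice varies. This stands, and no further statement of uncertainty is needed.
- **The direction is unknown.** A reader might infer that the wording pushes families towards longer IV treatment. The same sheet places long IV in the past and reports a move towards less antibiotic treatment overall, which could work the other way. The families also have recent experience of treatment.
- **The design softens the consequence.** No willingness rate is planned, reasons are asked for, and reactions to the labels can surface and be analysed.

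These arguments limit the point but do not remove it. Disclosure of uncertainty does not tell the reader which treatment 'standard' means. Probing can bring out a reaction to a label only if the family mentions it, whereas the label can simply be left out.

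**Conclusion.** The point holds as a wording fault on the adult and 13+ sheet: one value-laden label and one undefined reference term, placed just before a question that serves aim 3 and out of step with the stated lack of consensus. It creates a risk of framing. Whether framing occurs, in which direction and how strongly cannot be established from the document.

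The verdict rests on one assumption: that section 1.2 is the background sheet and process information to which section 1.3.5 refers. The matching content and sequence support this. The study's design and its clinical content are not affected, and the change is worth making because it costs almost nothing.

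**What to change.** In Protocol section 1.2:

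1. Delete the 'text book' sentence. The history reads complete without it.
2. Where the two groups of this trial are described, replace 'new' and 'standard' with the wording already on the cards: longer IV (later switch) and shorter IV (early switch). Use the same names in the process diagram if it does not already do so.
3. Keep one sentence that explains what a control group is, and state which of the two groups serves as the comparison. Aim 3 itself speaks of treatment and control, so this explanation should not be lost.

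The cost is one deleted sentence, a few changed words and a slightly longer explanation of the control group.

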1.3 Qualitative Study Topic Guide and Tools for Interviews

1.3.1 Risks and benefits prompt cards

LATER switch to oral antibiotics* (Longer IV treatment)

| Benefits | Risks |
|---|--|
| 
• Guaranteed delivery of the antibiotic• Treatment not dependent on child being willing to take medicine (or on remembering doses)• No drug gut absorption problems that sometimes happens in very ill children• Reliable treatment of the infection | 
• More time in hospital or under community nurse team• Disruption of daily activities• Risk of infection at site of IV line• Risk of displaced or blocked lines• Increased risk of reaction to antibiotic• Increased risk of side effects such as bone marrow suppression |

*Switch only made once pain, fever and infection (measured by a blood test) is reduced.

EARLY switch to ORAL antibiotics* (shorter period of IV)

Benefits

- Shortened stay in hospital (or daily visits by community nurse to give intravenous antibiotics)
- Reduced risk of infection at site of intravenous line (where drug is administered)
- Avoids problems with displaced or blocked lines
- Lower risk of reaction to antibiotic and side effects

Risks

- Reduced IV therapy may result in incompletely or inadequately treated bone or joint infection
- Incompletely or inadequately treated infection may rarely lead to chronic infection with destruction of cartilage, bone and growth plate, which can then cause permanent deformity and disability.

* Switch only made once pain, fever and infection (measured by a blood test) is reduced.

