The advantages of switching from intravenous to oral antibiotics are that the duration of hospital stay may be shortened. Additionally the risks of line-site infection and bacteraemia when a venous catheter is in place for antibiotic administration for prolonged periods are

reduced. Where used, these intravenous lines may need replacing if they become occluded or displaced necessitating hospital admission and often general anaesthetic for the procedure.

The advantage of prolonged intravenous therapy is guaranteed delivery of the antibiotic, not dependent on child or family-specific factors such as adherence or absorption. This allows more reliable treatment of invasive and potentially destructive infection.

Prolonged intravenous therapy may increase the risks of reaction to the antibiotic, and side effects such as bone marrow suppression. On the other hand, incompletely or inadequately treated bone or joint infection may rarely lead to chronic infection with destruction of cartilage, bone and growth plate, which can then cause permanent deformity and disability. However, whilst it may be desirable for many families to spend less time in hospital, with reduced duration of intravenous therapy, the perception of risks of complications secondary to potentially incomplete treatment may mean that a trial of shortened duration of antibiotics is not acceptable to parents and/or clinical stakeholders.

There has been little previous qualitative research exploring the views of paediatric patients or their parents about treatment for or the impact of acute bone and joint infections, or of the medical or surgical treatment family life during and after admission to hospital with infection in a previously healthy child. Additionally, evidence regarding patient and parent perception and understanding of risks of complications, disability or adverse effects of treatment remains anecdotal.

Importantly, the willingness of parents and patients to participate in a RCT, and what factors may influence this is not known, and will vary depending on proposed study design.

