1.3.2 Risks and benefits prompt cards 8-12 years

Longer IV (like treatment A)

Advantages

- Drug goes straight into your blood and treatment is reliable
- Don't have to remember to take it, or take medicine that tastes horrible!

Disadvantages

- More time in hospital or visits from nurse at home.
- You can get infections from the tube
- The tube might get blocked or knocked out of place.

Shorter IV (like treatment B)

Benefits

- Less time in hospital, or having nurse visit at home
- Can't get infections, blocked or knocked out of place (like a tube can!)

Risks

- May forget, or not want to take it
- This means the illness might not get completely better -
- Which could mean long term problems or disability.

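### The adult prompt cards give the serious harm of shorter intravenous treatment in full but leave out bacteraemia and the consequences of line failure on the longer intravenous side

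*Protocol*

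**What the plan says.** Protocol section 1 (Introduction and Background) sets out harms on both sides.

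- **Longer IV, infection:** "risks of line-site infection and bacteraemia when a venous catheter is in place for antibiotic administration for prolonged periods".
- **Longer IV, line failure:** where lines are used, "these intravenous lines may need replacing if they become occluded or displaced necessitating hospital admission and often general anaesthetic for the procedure".
- **Longer IV, drug effects:** "Prolonged intravenous therapy may increase the risks of reaction to the antibiotic, and side effects such as bone marrow suppression".
- **Inadequate treatment:** this "may rarely lead to chronic infection with destruction of cartilage, bone and growth plate, which can then cause permanent deformity and disability".

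The adult cards in section 1.3.1 cover the same ground. The later-switch card lists infection at the line site, "Risk of displaced or blocked lines", antibiotic reaction and marrow suppression. The early-switch card states: "Incompletely or inadequately treated infection may rarely lead to chronic infection with destruction of cartilage, bone and growth plate", and continues through to lasting deformity and disability.

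The card for ages 8-12 (section 1.3.2) says that infections can come from the tube and that "The tube might get blocked or knocked out of place". It says nothing of replacing the tube or of drug reactions and side effects.

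The adult guide (section 1.3.5, also used from age 13) shows the card at question 15. Part a asks which items strike the family and would be important to them. Part b asks again about willingness to join the trial and probes any change. Question 13 of the 8-12 guide (section 1.3.4) repeats the willingness question in the same way.

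**The concern.** The cards are the last information a family sees before the repeated willingness question. If one option's serious harm is spelled out to its end point while harms of the other stop at the triggering event, the stimulus is not even-handed.

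Two aims in section 2 are touched. Aim 2 seeks the outcomes that matter most to families, to inform the Delphi and stakeholder process. Bloodstream infection and an anaesthetic for line replacement cannot be picked out at question 15a if they are not on the card, and a family whose child's line never failed may not know of them. Aim 3 seeks views on accepting either randomised arm and what influences them. Section 1 itself expects that perceived risk of incomplete treatment could make a trial unacceptable to parents, so the balance of the risk information bears on the thing being studied.

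**Working it through.** No arithmetic on sample size, error rates or events applies: this is an interview study expecting about thirty families, with sampling to saturation. The check is a comparison of section 1 with the adult cards in section 1.3.1.

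| Harm in section 1 | Adult card |
|---|---|
| Line-site infection (longer IV) | Present |
| Bacteraemia (longer IV) | Absent |
| Line failure leading to hospital admission and often a general anaesthetic (longer IV) | Event present, consequence absent |
| Antibiotic reaction (longer IV) | Present |
| Marrow suppression (longer IV) | Present |
| Rare chronic infection with lasting disability (inadequate treatment) | Present almost verbatim, including the qualifier that it is rare |

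**Tally for longer IV.** 3 intact + 1 absent + 1 shortened = 5. The count depends on how the line-failure sentence is divided. If event, admission and anaesthetic are counted separately there are 7 items, and 4 of 7 appear. Neither count measures bias. Nor should either be set against a count of steps in the single disability chain, which is a different unit.

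**Does it matter which half of the card is shown?** Question 15 introduces the card as being about an early switch, and I assume that both halves are shown. If only the early-switch half were shown, the gap would remain: its benefits mention line-site infection and displaced or blocked lines, but not bacteraemia, admission or anaesthetic.

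**Wording that pulls the other way.** The early-switch card says line problems are avoided, although that option still begins with IV treatment. The 8-12 card similarly says that the shorter option cannot bring tube infections or blockages. The later-switch card lists 6 risks and the early-switch card 2. The 6 include time in hospital and disruption of daily life, so a bullet count does not settle severity.

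**The 8-12 card.** Its statement on infection is not limited to the site, so bloodstream infection is not clearly excluded. It gives no consequence of tube failure, omits drug reactions and side effects, shortens the disability outcome and drops the qualifier that it is rare. The near-verbatim reproduction is therefore a feature of the adult card only.

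**The question asked.** Question 15b concerns joining a randomised trial, not preferring an arm. Understating longer-IV harms could make shorter IV look worse by comparison, which might lower willingness. It could also make the longer-IV arm easier to accept, which might raise it. The sign is open.

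**The case against.** The strongest reply is that a prompt card need not reproduce a background section, that nothing on the card contradicts section 1, and that the later-switch card is not mild, since it keeps marrow suppression and antibiotic reaction. The design also limits the damage. All participants have lived through the illness. Adult questions 4, 5 and 9 draw out treatment, IV disadvantages and other problems before the card appears. Question 12a asks openly what matters in judging success. Willingness is asked before the card and again after it, with reasons probed. The guide is developed with patient and public contributors and piloted, and no numerical willingness estimate is stated that could be biased.

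Most of this stands, and it limits how serious the point is. It does not remove it. Families can raise only what they know, and probing a change of mind does not supply missing facts. A shift after the card is also where uneven content would show. The card's bullet on more time in hospital concerns duration of treatment and does not convey an admission and anaesthetic for a failed line.

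A reader might infer that the cards drop all the serious harms of longer IV, or that they bias the willingness answer against shorter IV. The documents support neither. Serious drug harms are kept, some wording favours shorter IV, and the willingness question is about trial entry.

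**Conclusion.** The adult cards describe the two options at unequal depth when measured against the protocol's own account. On the longer-IV side one harm is missing and one is cut to the event without its consequence, while the rare worst outcome of inadequate treatment is carried through to its end. Taken alone, these gaps understate the harms of longer IV in the material behind questions 15a and 15b. No size or net direction of effect on willingness to be randomised can be derived from the documents.

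The conclusion rests on reading section 1 as the sponsor's own statement of the harms, and on the cards being shown as printed. It is a modest point about the interview tool, worth correcting because the repair is cheap and the text already exists. For the 8-12 card, how much to tell a child is a judgement, and brevity there is defensible.

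**What to change.** **Adult later-switch card.** Replace the infection bullet with: *Risk of infection at the line site or in the bloodstream*. Keep "Risk of displaced or blocked lines" and add: *which may need replacing, meaning hospital admission and often a general anaesthetic*. Use hospital admission, as section 1 does, rather than readmission.

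**Adult early-switch card.** Mirror both items as reduced risks, in place of the present bullets on line-site infection and on avoiding line problems.

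**8-12 card.** Consider, with the patient and public contributors, age-appropriate wording on tube replacement and on medicine side effects. No particular phrase is needed from the statistical side.

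**Cost.** A minor amendment and slightly longer cards. For the 8-12 card there may be one more unpleasant fact for a child to hear, which is why that wording should be settled with the contributors. If interviews have already used the present cards, record which version each family saw.
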